5.2 Analysis Populations

The safety population is defined as all patients who receive at least one full or partial infusion of Replagal. All safety analyses will utilize the safety population.

5.3 Patient Disposition

Patient disposition, including the number of patients who signed informed consent, were included in the safety populations, completed or discontinued the study, and the primary reason for discontinuation will be tabulated by cohort, previous Enzyme Replacement Therapy (ERT) status, and overall, along with percentages. Percentages will be based upon the total number of patients in the safety population.

A patient listing will be presented for the safety population, showing study completion/termination status. Additionally, a patient listing will be presented for any consented patients with any inclusion, exclusion and eligibility violation showing whether the patient met eligibility criteria, along with the results of each inclusion and exclusion criteria, and whether any exemptions were granted.

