7 STATISTICAL METHODS

No formal statistical tests will be conducted. Tabular summaries of patient baseline demographic and clinical characteristics, patient disposition, medical history, physical examination, vital signs, AEs, anti-agalsidase alfa antibody, and infusion information will be produced for the safety population. The safety population includes all patients who receive at least 1 full or partial infusion of Replagal. Continuous data collected prior to receiving study drug and at subsequent visits will be summarized using descriptive statistics (n, mean, median, minimum, maximum, and standard deviation). Categorical data will be summarized as frequencies and percentages. All data summaries will be presented for each cohort and overall all as appropriate, unless otherwise indicated.

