7.2 Patient Disposition

The disposition of all enrolled patients will be summarized with frequencies and percentages including patients who completed the study and patient who discontinued study treatment prior to the end of study visit.

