5 STATISTICAL ANALYSIS

5.1 General Methodology

All analysis will be performed by the Biometrics Department, Shire HGT using SAS[®] Software version 9.3 or higher (SAS institute, Cary, NC, USA). All study data will be presented in by-patient data listings.

No formal statistical tests will be conducted. Tabular summaries of patient baseline demographic and clinical characteristics, patient disposition, medical history, vital signs, AEs, anti-agalsidase alfa antibody, and infusion information will be produced for the safety population. The safety population includes all patients who receive at least one full or partial infusion of Replagal. Continuous data collected prior to receiving study drug and at subsequent visits will be summarized using descriptive statistics (n, mean, median, minimum, maximum, and standard deviation). Categorical data will be summarized as frequencies and percentages. All data summaries will be presented for each cohort and overall, as appropriate, unless otherwise indicated

Cohort:

Cohort is defined as:

- Cohort 1: Patients from CFDI and receiving Replagal on EOW regimen
- Cohort 2: Patients who participated in REP001a and receiving Replagal on weekly regimen

Data Derivations:

The following key derived and computed variables have been initially identified. It is expected that additional variables may be required. The SAP will not be amended for additional variables. All derived and computed variables, including additional variables later identified, will be documented in the “Define Document,” and also in the SAS analysis dataset creation programs. The following are anticipated data derivations:

- *Screening period:* Within 6 months prior to first dose
- *Pre-treatment period:* Prior to first study drug infusion
- *Day 1:* Day of first study drug infusion
- *Date of Enrollment (entry):* Date informed consent is signed
- *Baseline:* Last valid non-missing assessment made prior to the first study drug infusion.
- *Change from Baseline:* Post-baseline value – Baseline Value

- *% Change from Baseline:* $\{(Change\ from\ Baseline / Baseline) * 100\}$
- *Change from Pre-infusion:* Value immediately after infusion – value immediately before infusion.
- *% Change from Pre-infusion:* $\{(Change\ from\ pre-infusion / pre-infusion) * 100\}$
- *Age:* integer of $\{(date\ of\ informed\ consent - date\ of\ birth) / 365.25\}$
- *Duration of study drug exposure:* (Date of last infusion – date of first infusion)+1

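### SAP 5.3 divides every disposition row, including patients who signed consent, by the number treated, so the consent row exceeds 100% if any consented patient is not dosed

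*SAP*

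**What the plan says.** SAP 5.3 sets out the rows of the disposition table: "Patient disposition, including the number of patients who signed informed consent, were included in the safety populations, completed or discontinued the study", together with the main reason for stopping. The table is presented by cohort, by previous ERT status and overall. One denominator is given, with no exception for any row: "Percentages will be based upon the total number of patients in the safety population".

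Two definitions elsewhere in the SAP fix how these groups nest. In SAP 5.2, "The safety population is defined as all patients who receive at least one full or partial infusion of Replagal". In SAP 5.1, the date of enrolment is "Date informed consent is signed". Enrolled therefore means consented, and treated patients are a subset of the enrolled.

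The protocol gives two different bases. Protocol 7.2 states: "The disposition of all enrolled patients will be summarized with frequencies and percentages". The opening paragraph of Protocol Section 7 lists disposition among other summaries ("Tabular summaries of patient baseline demographic and clinical characteristics, patient disposition, medical history, physical examination, vital signs" and so on) and ends the list with "infusion information will be produced for the safety population". The protocol synopsis and SAP 5.1 also place disposition in the safety population.

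**The concern.** A percentage describes a part of a whole. In this table the first row counts a larger group than the denominator, so its percentage can pass 100%. The second row is the denominator divided by itself, so its percentage carries no information.

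Consented but undosed patients are foreseeable in this study. Screening data may be gathered "Within 6 months prior to first dose" (SAP 5.1). Protocol 6.1 has eligibility determined before the first dose, and Protocol 6.13 allows withdrawal at any time. The SAP itself makes provision for the interval: SAP 5.7.1 defines pre-treatment adverse events between consent and first infusion, and SAP 5.3 plans a listing of consented patients with eligibility violations.

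At stake is the clarity of the table that tells a reader how many enrolled patients the safety results represent, and how many stopped. There is also a gap in the numerator, because the SAP does not state whether someone who leaves before dosing belongs in the discontinued row.

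**Working it through.** The plan gives no disposition figure to reproduce. Its one computed design figure, in SAP 3.6, is at least a 95% chance of seeing one or more events of 5% frequency in 60 patients. It checks: 1 − 0.95^60 = 0.954. It has no bearing on this point, except that 60, the planned minimum, is a convenient size for illustration.

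**Inputs**
- N_S: patients in the safety population. Taken as 60 and 200, the planned minimum and maximum (SAP 3.1).
- u: consented but undosed patients. Not given in the documents; assumed 0, 1, 3 or 7 for N_S = 60 (0% to about 10% of those consented), and 22 for N_S = 200.
- N_C = N_S + u: consented, hence enrolled.
- D: treated patients who discontinue. Not given; assumed 20% of N_S (12 of 60, 40 of 200). All other treated patients are taken to complete.

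**Formulas**
- Consent row under SAP 5.3: N_C / N_S
- Safety-population row under SAP 5.3: N_S / N_S = 100%
- Discontinued, pre-dose withdrawals counted, SAP denominator: (D + u) / N_S
- The same numerator over all enrolled: (D + u) / N_C
- Discontinued, treated patients only, SAP denominator: D / N_S

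**Results**

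| N_S | u | Consent row | (D+u)/N_S | (D+u)/N_C | D/N_S |
|---|---|---|---|---|---|
| 60 | 0 | 60/60 = 100.0% | 12/60 = 20.0% | 12/60 = 20.0% | 20.0% |
| 60 | 1 | 61/60 = 101.7% | 13/60 = 21.7% | 13/61 = 21.3% | 20.0% |
| 60 | 3 | 63/60 = 105.0% | 15/60 = 25.0% | 15/63 = 23.8% | 20.0% |
| 60 | 7 | 67/60 = 111.7% | 19/60 = 31.7% | 19/67 = 28.4% | 20.0% |
| 200 | 22 | 222/200 = 111.0% | 62/200 = 31.0% | 62/222 = 27.9% | 20.0% |

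If pre-dose withdrawals are counted as discontinued, completed plus discontinued also passes 100%. With u = 3 it is (48 + 15)/60 = 105.0%.

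The table is split by cohort and previous ERT status, so a single undosed patient weighs more in a small column. If each column uses its own safety-population count, an assumed column of 10 treated and 1 undosed gives 11/10 = 110%.

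**The case against.** The strongest reply is that little harm follows, and most of it stands.

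- **The treated fraction is not lost.** A reader might infer that the table hides it. SAP 5.3 tabulates both counts, so 60 of 63 (95.2%) can be worked out directly. What is missing is a row that reports it.
- **An inflated discontinuation rate is not established.** A reader might infer that untreated withdrawals inflate it. That depends on a numerator the SAP leaves open, and the documents lean the other way. Protocol 7.2 speaks of patients who stopped study treatment, and the completion listing in SAP 5.3 covers the safety population only. With treated patients only, 12/60 = 20% is a valid rate among the treated. It would then understate total attrition among the enrolled (15/63 = 23.8%), not overstate it.
- **The SAP does not simply depart from the protocol.** A reader comparing SAP 5.3 with Protocol 7.2 alone might think so. Protocol Section 7 and the synopsis both support the safety population, so the inconsistency lies within the protocol.
- **Undosed patients may be few or none.** Protocol Section 3 has patients begin to enrol once criteria are met and consent is obtained, which limits screen failures after enrolment.

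None of this rescues the consent row. A treated-only denominator cannot suit a row that counts all consenters, whichever protocol statement is followed. Nor do the listings in SAP 5.3 clearly fill the gap: one covers the safety population and the other covers eligibility violations, so an eligible patient who withdrew before dosing would appear in neither. The general promise in SAP 5.1 to list all study data might capture such a patient, but no listing is specified for this group.

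**Conclusion.** The point holds as a small reporting error. As written, SAP 5.3 gives a consent row above 100% as soon as one consented patient is not dosed (101.7% with 1 against 60 treated, 105.0% with 3, 111.7% with 7) and a safety-population row fixed at 100%. Whether the discontinuation percentage is affected is conditional. If pre-dose withdrawals are counted, it exceeds the all-enrolled figure by 0.4 points (u = 1) to 3.3 points (u = 7) at 60 treated, under the assumed 20% discontinuation. If they are not counted, the rate is valid for treated patients.

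These sizes rest on assumed numbers of undosed and discontinued patients, because the documents give neither. With no undosed patients every percentage is correct. No formal test is planned and all safety analyses use the safety population, so no safety result changes.

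**What to change.** In SAP 5.3, replace the single denominator with one for each group of rows:

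- Consented, treated and not treated: all consented (enrolled) patients.
- Completed, discontinued and reason for discontinuation: the safety population, counting treated patients only.
- Withdrawals between consent and first dose: a separate row, with reasons.

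Every enrolled patient is then accounted for, the treated fraction is reported, and the existing base for outcomes of treated patients is kept.

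Reconcile Protocol 7.2 (all enrolled patients) with Protocol Section 7 and the synopsis (safety population). A short note in SAP 6.3 could record which base applies to which rows.

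The cost is a few sentences in the SAP and changed denominators in one table. No new data collection is needed for the denominators, because both counts are already tabulated; the extra row needs the reason for each pre-dose withdrawal to be on record.

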5.4 Protocol Deviations

Shire defines a protocol deviation as an incident involving noncompliance with the protocol, but one which typically does not have significant effects on the patient's rights, safety, welfare, or the integrity of the resultant data. Patient records will be examined on a case-by-case basis prior to database lock to determine if they have violated conditions set forth in the study protocol. Protocol violations are defined as more serious deviations that may affect the subject's rights, safety, or welfare, or the integrity of the resultant data or any serious deviation that affects the collection of data for a primary endpoint.

Patients in the safety population having protocol deviations will be presented in data listings.

5.5 Demographics and Other Baseline Characteristics

5.5.1 Demographics

Demographics and baseline characteristics will be summarized by cohort, age group, previous ERT status and overall based on the safety population. Descriptive statistics will be summarized for age at informed consent, baseline height (cm), baseline weight (kg), and duration of Fabry disease (years). Frequencies and percentages will be tabulated for sex, race, ethnicity, and age group.

5.5.2 Medical/Surgical History

Medical/Surgical history will be summarized by cohort, previous ERT status and overall based on safety population. The number and percentage of patients with medical history in any and each body system will be tabulated.

5.5.3 Fabry Disease Treatment History

Fabry disease treatment history will be summarized by cohort and overall based on safety population. The method of Fabry confirmation, the number and percentage of patients with previous treatment with Fabrazyme, and with previous treatment with Replagal will be tabulated, along with descriptive statistics on the duration (in months) and dose of the previous treatment.

5.6 Treatment Compliance and Extent of Exposure

Treatment compliance and extent of exposure will be summarized by cohort, previous ERT status and overall based on the safety population. The number of infusions initiated, missed (uninitiated), partial, and complete, average infusion time (in minutes) initiated and completed, duration of exposure to Replagal AF both in days and weeks, and cumulative dose of study drug taken will be summarized using descriptive statistics.

5.6.1 Primary Endpoint

Not applicable

5.6.2 Secondary Endpoints

Not applicable

5.6.3 Subset Analyses

Although no subgroup analysis is explicitly indicated in the study protocol, subgroup analyses by sex group, age group, previous ERT status, anti-drug antibody (ADA) status and neutralizing antibody (NAb) status will be performed, as applicable. Subgroups of age group, previous ERT status, ADA status and NAb status are defined as:

Age group (years) is defined as:

- <18
- ≥18

Previous ERT status is defined as:

- Previously on Fabrazyme (switched)
- Previously on RB Replagal
- Treatment-Naïve
- Other (including the patients who were previously on Fabrazyme and Replagal, on Replagal RB and Replagal AF, and whose ERT status is unknown)

ADA status is defined as:

- Positive: At least one positive test for ADA during the study evaluation period
- Negative: No positive test for ADA during the study evaluation period

NAb status is defined as:

- Positive: At least one positive test for NAb during the study evaluation period
- Negative: No positive test for NAb during the study evaluation period

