3 STUDY DESIGN

3.1 General Description

This is an open-label, single-arm, multicenter, Phase III/IV safety study and is designed to evaluate the safety of Replagal in Canadian patients with Fabry disease. All patients may continue to receive Replagal in this treatment plan until Replagal AF is commercially available for the patient, the patient's participation or the study is discontinued, whichever comes first. Safety data will be collected throughout the treatment protocol.

A minimum of 60 patients with Fabry disease and up to 200 patients are expected to participate in this protocol. Two cohorts are included in the protocol; Cohort 1 is for patients from the Canadian Fabry Disease Initiative (CFDI) and provides Replagal treatment on an every other week (EOW) regimen and cohort 2 is only for patients who participated in REP001a and provides Replagal treatment on a weekly regimen. Patients may begin to enroll in the treatment protocol as soon as the eligibility criteria are fulfilled and informed consent is obtained.

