The number and percentage of patients reporting IRRs will be tabulated for any IRR, and by SOC and PT by cohort, previous SRT status, age group, sex and overall based on the safety population. IRRs by SOC and PT will be tabulated by severity and cohort, by serious and cohort, and by closest relationship. In addition, the number and percentage of patients with at least one, and no IRRs will be tabulated by anti-drug antibody (ADA) status and neutralizing antibody (NAb) status status.

The number and percentage of patients reporting SAEs will be tabulated for any SAE, and by SOC and PT by cohort, previous SRT status, age group, sex and overall based on the safety population. In addition, SAEs by SOC and PT will be tabulated by severity and relationship by cohort, separately.

The number and percentage of patients reporting TEAEs that led to permanent discontinuation will be tabulated for any TEAE, and by SOC and PT by cohort, previous ERT status, age groups and overall.

Separate data listings will be presented showing all SAEs, deaths, and TEAEs leading to treatment discontinuation.

All AEs will be listed by patient for the safety population and those AEs considered to be treatment-emergent, as well as IRRs will be flagged as such.

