5.7.5 Anti-agalsidase alfa Antibody Results

Serum samples will be collected for evaluation of anti-agalsidase alfa antibodies within 6 months prior to the patient receiving the first dose of Replagal and at the biannual or annual safety visits, as applicable. Analysis of anti-agalsidase alfa antibodies will be performed using a validated electrochemiluminescent (ECL) immunoassay following a tiered approach (screening, confirmatory, and titer). Samples that are confirmed positive for the presence of anti-agalsidase alfa antibodies will be further evaluated for the presence of neutralizing antibodies using an enzyme inhibition assay.

Anti-agalsidase alfa antibody data are obtained from 2 different testing schemes. Anti-agalsidase alfa antibody samples collected were initially tested (prior to Nov 2014) following a tiered approach at Shire and results were reported by isotype. First, all samples were screened using enzyme linked immunosorbent assays (ELISAs) for the presence of anti-agalsidase alfa Immunoglobulin G (IgG), Immunoglobulin A (IgA), Immunoglobulin M (IgM), and Immunoglobulin E (IgE) isotype antibodies. When a sample met the IgG, IgA, IgM, or IgE positive cut-point criteria, the appropriate ELISA was used to confirm the presence of antibodies and to determine titer. Samples confirmed with the presence of anti-agalsidase alfa IgG, IgA, IgM, or IgE antibodies were further evaluated for presence of Nab using an enzyme activity based neutralization assay. During 2014, a new test method was developed and validated at a contract research organization. The later time point samples were first screened using an ECL bridge assay. Samples screened “positive” are then confirmed by competition with agalsidase alfa in the ECL bridge format. The titer of confirmed positive samples is then determined using the same ECL bridge assay, and all confirmed positive samples are further characterized using the enzyme activity based neutralization assay.

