The number and percentage of patients who become positive for any antibody isotype, each isotype, and NAb will be tabulated at baseline, at each biannual visit and overall. Shift tables of status of any antibody isotype and Nab from baseline to each biannual visit will be presented based on a classification of observations as Positive, Negative, and Not Available (NA). Both IgG and ADA data will be referred to as ADA data for the convenience of presentation. For ADA, the change in titer for antibody positive patients from baseline to each biannual visit will be summarized. These analyses will be done for the safety population overall, by cohort, and by previous ERT status.

All anti-agalsidase alfa antibody data will be listed, a listing of patients who became ADA, NAb, and IgE positive will be provided.

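### ADA and NAb Negative mean only that no positive test exists, so the table of infusion reactions by antibody status mixes patients lacking a relevant result with tested negatives and ignores which came first

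*SAP*

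**What the plan says.** SAP 5.6.3 gives ADA and NAb status two levels each. Positive is at least one positive test in the study evaluation period. Negative, for ADA, is "Negative: No positive test for ADA during the study evaluation period", with the same form for NAb. The term study evaluation period is used only there. SAP 5.1 defines screening and pre-treatment periods, and Protocol 6.10.4.1 defines a period of observation for adverse events, but neither is linked to it.

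SAP 5.7.1 plans that "the number and percentage of patients with at least one, and no IRRs will be tabulated by anti-drug antibody (ADA) status and neutralizing antibody" status. The population is the safety population, "all patients who receive at least one full or partial infusion of Replagal".

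On NAb testing, SAP 5.7.5 says that "all confirmed positive samples are further characterized using the enzyme activity based neutralization assay". It also says that "Anti-agalsidase alfa antibody data are obtained from 2 different testing schemes", an isotype ELISA first and an electrochemiluminescent (ECL) assay later, and that "Both IgG and ADA data will be referred to as ADA data for the convenience of presentation". The same section has a Not Available class, but only for the shift tables by visit.

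The schedules in both documents place antibody samples before the first dose and at biannual or annual visits. The End of Study column marks only adverse event assessment, and Protocol 6.13 gives withdrawing patients the End of Study evaluations. Follow-up is open-ended: "All patients may continue to receive Replagal in this treatment plan until Replagal AF is commercially available for the patient", subject to discontinuation of the patient or the study.

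**The concern.** A two-level status defined by the absence of a positive result cannot tell a negative result from no result. Three things follow from the wording.

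1. A patient who leaves before the first biannual or annual visit has no scheduled on-treatment antibody result, yet falls into Negative unless a positive pre-dose sample counts. Patients withdrawn after a reaction could be among them.
2. NAb is run only on confirmed positive samples, so NAb Negative contains patients never tested for NAb by design together with ADA-positive patients who tested NAb-negative. This needs no assumption about rates.
3. Status covers the whole study and has no date condition. An IRR that preceded the first positive sample counts under Positive. Longer follow-up also raises the chance of ever being positive and of ever having an IRR, so unequal follow-up can link the two where no link exists.

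This is the only planned summary that relates antibodies to infusion reactions, and SAP 1.2 says that the SAP's analyses will go into regulatory submissions.

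**Working it through.** The documents give no antibody rate, IRR rate or distribution of follow-up, so every rate below is an assumption. The only computed figure in the SAP is the detection probability in 3.6. It reproduces (1 − 0.95^60 = 0.954), and this point does not depend on it.

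**Unequal follow-up, no true link.** Let t be follow-up, uniform over a range; h the hazard per year, the same for first positive and first IRR; and p0 the share positive at entry, with the pre-dose sample counted. Then P(t) = p0 + (1 − p0)(1 − e^(−ht)) is the chance of being Positive and Q(t) = 1 − e^(−ht) the chance of an IRR. The table's risk ratio (RR), Positive over Negative, is {E[PQ]/E[P]} / {E[(1 − P)Q]/E[1 − P]}. Example: h = 0.10, p0 = 0.2, t from 1 to 5 years gives IRR risks of 0.269 and 0.244, so RR = 1.10. For h from 0.05 to 0.20:

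| p0 | t 1–5 years | t 0.25–5 years |
|---|---|---|
| 0 | 1.15–1.17 | 1.29–1.35 |
| 0.2 | 1.07–1.13 | 1.12–1.26 |
| 0.4 | 1.04–1.11 | 1.07–1.21 |

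Equal follow-up gives 1.00. A harsher case has p0 = 0, h = 0.10, half the patients followed 4 years and half 0.5 year: 0.293/0.165 = 1.78. With 1 or 2 years in place of 0.5, it is 1.42 or 1.12.

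**Order of events.** With equal hazards and p0 = 0, the IRR comes first in half of the patients who have both events. With baseline positives the share is (1 − p0)·½E[Q²] / (p0·E[Q] + (1 − p0)·E[Q²]). For h = 0.10 and t from 0.25 to 5 years, E[Q] = 0.2236 and E[Q²] = 0.0613. The share is then 0.0245/0.0937 = 26% at p0 = 0.2 and 0.0184/0.1262 = 15% at p0 = 0.4. This assumes that a positive is detected at once.

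**No on-treatment sample.** Follow-up is uniform over 0.25 to 5 years.

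- Biannual visits: a first sample at exactly 6 months gives (0.5 − 0.25)/4.75 = 5.3%. A first sample uniform over 0 to 6 months gives (0.03125/4.75)/0.5 = 1.3%.
- Annual visits: a first sample at exactly 12 months gives (1 − 0.25)/4.75 = 15.8%. A first sample uniform over 6 to 12 months gives (0.75 − 0.25)/4.75 = 10.5%.
- If everyone is followed for at least 1 year, nobody lacks a sample.

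**Effect of counting them Negative.** Assume 20% of sampled patients are positive, with IRR risks of 30% in positives and 10% in negatives (true RR 3.0). Let u be the unsampled share and r its IRR risk. The Negative row shows [(1 − u)(0.8)(0.10) + u·r] / [(1 − u)(0.8) + u]. With r = 0.30 and u = 0.05, that is 0.091/0.81 = 0.112, so RR = 2.67. With u = 0.10 or 0.20 it is 2.41 or 2.03. With r = 0.10 it stays at 3.00.

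**Sampling noise.** With 30% positive and an overall IRR risk of 16%, SE(log RR) = √[(0.84/0.16)(1/n₁ + 1/n₀)]. At N = 60 (18 and 42 patients) it is 0.645, so the 95% limits are ×/÷ e^(1.96 × 0.645) = 3.5. At N = 200 (60 and 140) it is 0.354, giving ×/÷ 2.0.

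**The case against.** The best case against the point is that it asks for little that matters.

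- The SAP nowhere states that patients without an on-treatment result are Negative. SAP 7.2 rules out imputation, and 5.7.5 has a Not Available class. That stands as a caution: the finding rests on a literal reading. But 7.2 supplies no class for such patients, 5.6.3 offers only two, and the class in 5.7.5 does not reach the IRR table.
- Listings will show antibody results and flagged IRRs, so sequence can be checked by hand. This is true, but no planned table shows it.
- NAb-negative counts among ADA-positive patients can largely be had by subtracting one table from the other. This also holds, apart from patients who reached NAb testing through other isotypes, but a reader should not have to do it.
- Sampling noise exceeds the bias and no formal test is planned (SAP 5.1). That stands and limits the weight of the point.

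A reader might infer more than the documents support:

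- **That many patients are wholly unsampled.** A pre-dose sample is required of everyone, so the group is those without an on-treatment result. The 5% and 16% shares are upper cases for the assumed follow-up, because visits follow the existing schedule of the Canadian Fabry Disease Initiative (SAP 3.2). Annual visits became possible only with Amendment 5, so 16% cannot be applied to all 200 patients.
- **That a patient positive only for IgA, IgM or IgE has no stated ADA status.** SAP 5.7.5 implies that the ADA label covers IgG and ECL results only.
- **That the largest ratios are typical.** They assume nobody is positive at entry, although the protocol continues supply to patients already on treatment (Protocol 1.5).

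**Conclusion.** The point holds as a defect in the stated rule, and it should be corrected. The literal rule labels patients without an on-treatment result as Negative, merges two different kinds of NAb Negative, and ignores whether the IRR or the positive sample came first.

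On assumed inputs, unequal follow-up alone gives an RR of 1.04 to 1.17 (1 to 5 years) or 1.07 to 1.35 (0.25 to 5 years; 1.07 to 1.26 if 20 to 40% are positive at entry). About 1 to 5% of patients would lack an on-treatment sample under biannual visits and about 11 to 16% under annual visits, with follow-up of 0.25 to 5 years.

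The documents do not support the inference that the table will overstate, or will hide, a link between antibodies and reactions. Unequal follow-up raises the ratio, reactors who leave unsampled lower it, and the net direction is unknown. The table is descriptive and no error rate is affected. What is at stake is how the one antibody–IRR summary is read.

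**What to change.** In SAP 5.6.3 and 5.7.1:

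- **(a)** Define the study evaluation period as starting after the first dose, and class the baseline sample separately. State in 5.6.3 that ADA means IgG by ELISA or the ECL result, as 5.7.5 implies.
- **(b)** Require at least one valid post-baseline ADA result for Negative; otherwise show Not evaluable. For NAb, show ADA negative and not tested by design apart from ADA positive and NAb negative. An ADA-positive patient without a valid NAb result is Not evaluable. A patient confirmed only for IgA, IgM or IgE under the ELISA scheme was tested for NAb, so show that patient by the NAb result.
- **(c)** Split Positive into positive at baseline and treatment-emergent.
- **(d)** For patients not positive at baseline, add one descriptive table of IRRs per 100 infusions, with the number of patients having an IRR, before versus on or after the first positive sample. Give Not evaluable and baseline-positive patients their own rows, and footnote the assay of the first positive sample. Leave a split at 12 months to the listings unless event counts allow it.

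The cost is SAP wording and one table; no new sample or visit is needed. Parts (b) and (c) alone do not remove the follow-up effect: among patients not positive at baseline, the p0 = 0 row applies, 1.15 to 1.35 with no true link.

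Table (d) has limits. It will be sparse. In simulation with no true link (20% positive at entry, hazards 0.1 per year, samples every 6 months), the upper 97.5% point of its ratio is about 4 at N = 60 and about 2.2 at N = 200. It dates seroconversion only to the next visit. It stays partly mixed with time on treatment: if IRR risk is doubled in year 1, the simulated ratio with no true link is 0.67 to 0.80. It also does not account for premedication after a reaction (Protocol 6.11). A footnote should say so.

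### NAb Negative includes patients never tested for NAb, so the infusion-reaction table by NAb status can reflect antibody status rather than neutralisation

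*SAP*

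**What the plan says.** SAP 5.6.3 gives NAb status two levels: "Positive: At least one positive test for NAb during the study evaluation period" and "Negative: No positive test for NAb during the study evaluation period". ADA status has the same form, with "Negative: No positive test for ADA during the study evaluation period". Neither variable has a level for patients who were not tested.

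SAP 5.7.5 describes two assay schemes, and both restrict who reaches the NAb assay.
- Older ELISA scheme (before November 2014): "Samples confirmed with the presence of anti-agalsidase alfa IgG, IgA, IgM, or IgE antibodies were further evaluated for presence of Nab".
- Newer electrochemiluminescent (ECL) scheme: "all confirmed positive samples are further characterized using the enzyme activity based neutralization assay". Protocol 6.8 has the same rule.

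SAP 5.7.5 also says that IgG results from the older scheme and ADA results from the newer one will both be presented as ADA.

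SAP 5.7.1 uses the subgroups in one table: counts of patients with at least one IRR and with none "will be tabulated by anti-drug antibody (ADA) status and neutralizing antibody (NAb) status". Nothing limits the NAb part of that table to antibody-positive patients. The antibody and NAb shift tables in SAP 5.7.5, by contrast, do have a third class for results that are not available.

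**The concern.** A patient whose samples never confirm positive for antibodies has no NAb result, yet counts as NAb Negative. So does a patient with no usable sample. Both sit beside patients whose antibodies were tested and found not to neutralise. NAb Positive, in contrast, contains only patients with a confirmed antibody response.

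The two columns therefore differ in antibody status as well as in neutralisation. If patients with antibodies have more IRRs for any reason, the NAb columns will differ too, and the table cannot say which property is responsible.

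Safety is the study's only objective, SAP 1.2 says the analyses go into regulatory submissions, and SAP 7.3 lists infusion-related events and antibody status among the interim analysis endpoints. A reader of the report could take this table as evidence about neutralisation.

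**Working it through.** **Figures in the plan.** The documents give no antibody prevalence, NAb share or IRR rate, so there is no planned figure to reproduce for this table. The only sample-size figure is in SAP 3.6: with 60 patients and a 5% event, 1 − 0.95^60 = 0.954, which agrees with the stated minimum of 95%. The point does not depend on it.

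**Formula.** Let r0 be the IRR rate in antibody-negative patients and r1 the rate in antibody-positive patients, taken as the same whatever the NAb result (no effect of neutralisation). Let s be the untested share of NAb Negative. For simplicity, every patient has a usable sample.

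- NAb Positive rate = r1
- NAb Negative rate = s × r0 + (1 − s) × r1
- Apparent NAb difference = s × (r1 − r0)

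**Example.** Assume r0 = 5%, r1 = 20% and 60 patients (the planned minimum in SAP 3.1). Splits are antibody-negative / antibody-positive and NAb-negative / antibody-positive and NAb-positive.

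| Split | NAb Negative rate | s | Difference (points) | Ratio |
|---|---|---|---|---|
| 20/30/10 | (1.0 + 6.0)/50 = 14.0% | 20/50 = 40% | 6.0 | 20/14.0 = 1.4 |
| 30/15/15 | (1.5 + 3.0)/45 = 10.0% | 30/45 = 67% | 10.0 | 20/10.0 = 2.0 |
| 40/10/10 | (2.0 + 2.0)/50 = 8.0% | 40/50 = 80% | 12.0 | 20/8.0 = 2.5 |
| 50/5/5 | (2.5 + 1.0)/55 = 6.4% | 50/55 = 91% | 13.6 | 20/6.4 = 3.1 |

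Among antibody-positive patients the comparison is 20% against 20% in every row, a ratio of 1.0.

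**Wider range.** With antibody prevalence p and NAb-positive share q of the antibody-positive patients, s = (1 − p)/(1 − pq).

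- p = 0.5, q = 0.3: s = 0.50/0.85 = 58.8%
- p = 0.2, q = 0.7: s = 0.80/0.86 = 93.0%

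These are the extremes for p from 0.2 to 0.5 and q from 0.3 to 0.7, and they do not depend on total sample size. At r0 = 10% and r1 = 30%, the apparent difference is 0.20 × s = 11.8 to 18.6 points. At 10% and 20%, it is 0.10 × s = 5.9 to 9.3 points. If r0 = r1, it is zero.

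**The case against.** **The table is descriptive.** The SAP plans no formal tests and no interaction analyses, and it attaches no causal reading to NAb status. This stands, and it limits the consequence: no decision rule turns on the table. A descriptive table must still compare the groups that its labels name.

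**Counting antibody-negative patients as NAb-negative is normal under tiered testing.** A patient with no confirmed binding antibody is not expected to have a neutralising one, so NAb detected against NAb not detected is a legitimate split. This stands as description if labelled that way. It answers a different question from whether neutralisation matters among patients who have antibodies, and it does not cover patients with no sample.

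**The information is not lost.** Antibody data are listed by patient, IRRs are also tabulated by ADA status, and the SAP wording might mean a cross-tabulation. Subtracting NAb-positive from ADA-positive counts would give the missing group. Much of this stands: the fault lies in labelling and comparison, not in lost data. But the SAP does not say cross-tabulation, and the subtraction works only if every NAb-positive patient is also ADA-positive.

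A reader might infer that this nesting always holds. The SAP does not support it. Before November 2014 a sample positive only for IgA, IgM or IgE went to the NAb assay, while ADA from that period means IgG. Such a patient could be NAb-tested, even NAb-positive, and still be ADA-negative.

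**Conclusion.** The point holds as a defect of definition in one descriptive safety table. NAb Negative pools untested with tested-negative patients, and this follows from the SAP's own text without any assumption. The distortion of the IRR comparison is conditional: it appears only if antibody status is associated with IRRs, and it equals that association times the untested share of NAb Negative. Under the assumed 5% and 20% rates the apparent ratio is about 1.4 to 3.1. With no association it is 1.0, and only the mislabelling remains.

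Two stronger readings are tempting. One is that the table will show an antibody effect as a neutralisation effect. The documents give no IRR rate by antibody status, so this cannot be asserted. The other is that NAb Negative consists mostly of untested patients. That depends on antibody prevalence and NAb share, also not given; in the 20/30/10 split they are 40% of the group.

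**What to change.** In SAP 5.6.3 and 5.7.1, replace the two-level NAb status with four mutually exclusive levels:

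1. antibody-negative (not NAb-tested);
2. antibody-positive/NAb-negative;
3. antibody-positive/NAb-positive;
4. not evaluable (no valid sample in the study evaluation period).

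For this variable, define antibody-positive as confirmed positive by ECL or by any ELISA isotype (IgG, IgA, IgM or IgE). That matches who was sent to the NAb assay and gives the older non-IgG positives a place, which an IgG-based ADA definition would not. State that the NAb contrast is read among antibody-positive (NAb-tested) patients only.

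The cost is SAP wording and extra columns in one table, using data already collected. Cells become smaller: in the 40/10/10 split the contrast is 10 against 10 patients instead of 10 against 50, so it will be imprecise. No test, alpha or sample size changes.
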